In the European Union, oseltamivir, taken orally, zanamivir which is inhaled, peramivir which is a solution to be diluted and used as an infusion and now intravenous zanamivir, are the four approved neuraminidase inhibitors (NAIs). Early treatment of influenza with oseltamivir has been associated with a reduced risk of severe infection and of admission to intensive care units (ICU) for pregnant women [Meijer, 2015; Delgado-Rodriguez, 2012]. Prior to the last influenza pandemic of 2009 there were few data on NAI safety in pregnancy. A recent European study of population-based registers from Denmark, Norway and Sweden and France captured data reflecting increased uptake of NAIs in pregnant women following the 2009 pandemic. Data from prescription registers, capturing NAI exposure during pregnancy, were linked to birth registers capturing information on pregnancy outcomes. Exposure to NAIs during pregnancy was not associated with increased risks of neonatal outcomes including LBW, SGA, preterm birth, stillbirth, neonatal death and neonatal morbidity. First trimester exposure was not associated with an increased risk of congenital malformations [Graner, 2017]. Although 74% of the NAIs exposures during pregnancy were to oseltamivir, data specific for zanamivir (including 321 first trimester zanamivir exposures) were not reported separately. Several additional observational studies of inhaled zanamivir exposure in pregnancy, with sample sizes ranging from 50 to 180 inhaled zanamivir exposures during any trimester of pregnancy, have failed to report a significant increase in adverse pregnancy outcomes [Walker, 2014; Saito, 2013; Dunstan, 2014].

Pre-clinical studies in rats and rabbits have failed to identify increased risks for malformations, maternal toxicity, or embryotoxicity following intravenous (IV) administration of zanamivir at doses up to 90 mg/kg/day. A further embryofoetal development study following subcutaneous administration of zanamivir at doses of up to 80 mg/kg, 3 times daily (240 mg/kg/day), observed an increase in the incidence rates of a variety of minor skeleton alterations and variants in the offspring at systemic exposure greater than approximately 3 times the human exposure at the clinical intravenous dose (600 mg twice daily). In most instances, the individual incidence rate of each skeletal alteration or variant remained within the background rates of the historical occurrence in the strain studied.

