8.3.2. Outcome definitions

There are three groups of outcomes of interest:

Maternal outcomes

• Maternal death during pregnancy and up to 42 days after delivery.

Pregnancy outcomes

- Live birth defined as an infant born alive.
- Spontaneous abortion (SAB) in clinically recognized pregnancies defined as foetal death or expulsion of products of conception prior to 20 weeks' gestation, or if gestational age is unknown, weighing less than 500g.
- Stillbirths defined as a foetal death occurring at 20 weeks' gestation or greater, or if gestational age is unknown, a foetus weighing 500 g or more.
- IAB defined as voluntary interruption of pregnancy, including pregnancy termination that occurs electively, to preserve maternal health, or due to foetal abnormalities.

Birth outcomes

- Prematurity defined as an infant born at gestational age <37 weeks.
- SGA defined as an infant born with a birth weight less than the 10th centile for the corresponding gestational age.
- LBW defined as an infant whose birth weight is <2500 g.
- Neonatal death defined as death of the infant within 28 days of birth.
- Major congenital malformation (MCM) defined according to EUROCAT criteria
- EUROCAT includes all major structural malformations and chromosomal malformations. Minor anomalies are excluded (as defined in Section 3.2 of the coding guide) and cases with more than one malformation type are only counted once for the calculation of overall malformation prevalence.

Maternal and infant follow up is proposed to 3 months after birth. Longer term follow-up is not proposed as there are no pre-clinical or clinical data to suggest a signal for developmental delay. Hence, it is impossible to determine an appropriate longer term follow up period which differs substantially according to the type of developmental adverse outcome of interest. As the majority of major malformations are detected at birth, a three month follow up period is deemed adequate to maximize capture of major malformations.

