IV zanamivir exposure will be further categorized by earliest trimester of exposure. For this registry, gestational weeks will be estimated from the most reliable EDD as reported by the HCP. If a CEDD is provided by the HCP, it will be used instead. The date of conception will be calculated as the most reliable EDD/CEDD minus 38 weeks. If the EDD is not available or never estimated, the first day of the LMP may be used to estimate gestational age. The second trimester will be considered to begin at week 14 after the date of conception or LMP, and the beginning of the third trimester, at week 28. If there is a discrepancy between gestational age calculated from LMP and reported gestational age, the HCP will be asked to verify the data.

If HCPs provide de-identified data to the registry, they must be able to verify the date of exposure to IV zanamivir. Such data may come from data collected both within and outside of the UKOSS/INOSS network. For example, UKOSS has ethical approval to collect a minimum exposure and outcome dataset on women exposed to new influenza treatments (including IV zanamivir) with a waiver of informed consent. This will enable capture of some data on women who may be exposed to IV zanamivir during hospitalisation with complicated influenza, but do not consent to participate in this study with more complete data collection. A similar situation may arise with other INOSS centres. Other potential de-identified data sources include anonymised healthcare data sources.

Outcome operational definition

All outcome variables will be provided by research staff at sites. They will be asked to describe any MCMs observed in the infant or foetus and will also be asked to report the

gestational age and birth weight. These two variables will be used to calculate preterm birth, LBW, and SGA. Data will be abstracted from medical records. As described above a teratologist/ geneticist will review all reported congenital anomalies and classify them using the EUROCAT system [EUROCAT, 2017].

Operational variable(s) definition

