The study staff will provide prenatal data (LMP, EDD, and CEDD), prenatal test data (test, date of test, and result), obstetrical history (previous pregnancies, live births, stillbirths, SABs, IABs, births with MCMs, and family history of MCMs), concurrent medical conditions, concomitant teratogenic medications, and tobacco use during pregnancy through the UKOSS/INOSS system. At pregnancy outcome, research staff will provide pregnancy outcomes data (live birth, stillbirth, SAB, IAB) and infant outcome (gestational age, birth weight, congenital malformations, gender and multiple gestation).

De-identified healthcare data:

If HCPs provide de-identified data to the registry, they will provide required data on maternal characteristics, prenatal data, obstetrical data, and pregnancy outcome data. De-identified data sources may include de-identified data collected under waiver of consent through the UKOSS/INOSS system or de-identified/anonymised healthcare electronic medical record sources where it is possible to identify this exposures and outcomes information.

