8.6.2. Resourcing needs

The implementation, management and closure of this study will be outsourced to a CRO, OXON Epidemiology. The study will be overseen at GSK by a PhD level Epidemiologist and a Study Delivery Lead.

Biostatistical and methodological issues will be addressed by a senior level statistician with expertise in observational data either from the CRO, or similar, or from within GSK.

8.6.2.1.	Timings of Assessment during follow-up
----------	--

Information requested	Registration provided by HCP	Pregnancy outcome provided by research staff up to 3 months post- delivery	Targeted follow up to collect information not previously obtained, provided by research staff
Maternal contact	Х	Xa	
information, alternate			
contact information, HCP			
contact information			
Maternal characteristics	Х		
(age,ethnicity, etc.)			
Maternal prenatal	Х	Xa	
information (LMP, EDD,			
CEDD, prenatal test			
results and timing)			
Obstetrical history	Х		Xp
Family history of MCMs	X		Xb

Information requested	Registration provided by HCP	Pregnancy outcome provided by research staff up to 3 months post- delivery	Targeted follow up to collect information not previously obtained, provided by research staff
IV zanamivir exposure information	X	Xa	
Influenza episode clinical details	X	Xa	
Pregnancy complications	Х	Xa	
Other Concurrent conditions and concomitant medications, tobacco use during pregnancy	X	Xa	
Pregnancy status		Х	
Outcome information (maternal death, live birth, still birth, SAB, gestational age, birth weight)		X	Xp
MCM noted and description		X	Xp

Abbreviations: CEDD = corrected estimated date of deliver; EDD = estimated date of delivery; HCP =health care provider; LMP = last menstrual period; MCM(s) = major congenital malformation(s); Ob =obstetric; SAB = spontaneous abortion.

a Obtain updated information since the previous contact.

b Targeted follow-up is designed to collect addition information (if necessary) to facilitate characterization of the foetal loss, MCMs and/or neonatal death.

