As EUROCAT includes chromosomal malformations and MACDP excludes chromosomal malformations, all malformations types will be collected through the registry and the appropriate comparisons will be made with and without chromosomal malformations. There will also be alignment of denominators around inclusion of foetal losses to ensure appropriate comparisons are being made between external reference groups and the registry. Pregnancies exposed to major teratogens (see Section 8.3.3) will be excluded from analyses.

If it is feasible, descriptive comparisons between the registry and an appropriate internal and/or external comparison group will be examined (see Section 8.2 for a description of potential reference groups).

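### The protocol is inconsistent on whether sites report major malformations or all congenital anomalies; if the form follows the narrower wording, site staff judge 'major' before the teratologist and MCM prevalence can only be biased low

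*Protocol*

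**What the plan says.** Two descriptions of the intake stand side by side in the protocol.

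**Narrow wording.**
- Section 8.4, outcome operational definition, on research staff at sites: "They will be asked to describe any MCMs observed in the infant or foetus".
- The table in section 8.6.2.1, which section 8.4 names as the summary of what is collected and when, has one relevant row: "MCM noted and description". Its footnote on targeted follow-up covers foetal loss, MCMs and neonatal death.

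**Broad wording.**
- Section 8.4, operational variable definitions, lists what research staff provide at pregnancy outcome: "infant outcome (gestational age, birth weight, congenital malformations, gender and multiple gestation". The word major is absent.
- Section 8.4, outcome operational definition, a few sentences after the narrow request: "a teratologist/ geneticist will review all reported congenital anomalies and classify them using the EUROCAT system".
- The objective in section 7 is congenital malformations, again without major.
- Section 8.7.1 states that "all malformations types will be collected through the registry", in a paragraph about comparisons with and without chromosomal malformations.

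**Endpoint.** Section 8.3.2 defines MCM by EUROCAT criteria: "Minor anomalies are excluded (as defined in Section 3.2 of the coding guide"). Section 8.7.1 restricts the primary analysis to cases that meet those criteria.

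**The concern.** The EUROCAT major/minor distinction comes from a coding guide. Sections 8.4 and 8.6.1 give its application, or at least its review, to a teratologist/geneticist. That arrangement works only if the specialist sees the anomalies before they are sorted. A form that asks for MCMs makes site staff sort first.

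The two kinds of site error are not equally correctable. If a site reports a minor anomaly as major, the specialist removes it. If a site takes a true MCM for minor and does not report it, nothing brings it back. Targeted follow-up starts from reported events, and an unreported anomaly does not show up as a missing field to query.

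The registry exists to pick up a prevalence above the reference. About 2 MCMs are expected in 100 live births at the reference rate (100 × 0.02), so single cases carry weight.

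**Working it through.** **1. Do the passages agree?** Read literally, the request and the table row cover MCMs. The list of infant outcome data covers congenital malformations. The specialist's task, reviewing and classifying anomalies by EUROCAT, presupposes an intake wider than MCMs. The statement in section 8.7.1 about all malformation types concerns chromosomal versus non-chromosomal types, so it does not clearly settle the question. The protocol does not say which wording governs the form.

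**2. Direction of the error.** Section 8.7.1 defines MCM prevalence as k/n. Here k is live births and foetal losses at 20 weeks or later with an MCM, and n is all live births plus foetal losses with an MCM.
- A missed MCM in a live birth turns k/n into (k − 1)/n.
- A missed MCM in a foetal loss turns k/n into (k − 1)/(n − 1), which is also below k/n whenever k < n.

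Both lower the estimate, and no path through this filter raises it.

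**3. The plan's own figure.** Inputs from section 8.5: N = 100 live births, reference p0 = 2%, 1-sided 5% error, 80% power, binomial distribution.
- Rule: the smallest r with P(X ≥ r | 100, 0.02) ≤ 0.05. P(X ≥ 5) = 1 − (0.1326 + 0.2707 + 0.2734 + 0.1823 + 0.0902) = 0.0508, which is too large. P(X ≥ 6) = 0.0508 − 0.0353 = 0.0155. So r = 6.
- Solving P(X ≥ 6 | 100, p1) = 0.80 gives p1 = 0.0779, and 0.0779 / 0.02 = 3.90.

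This reproduces the Table 1 entry of 3.90. The other 14 cells reproduce by the same method.

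**4. Effect of unreported MCMs (illustration).** Let s be the share of true MCMs that sites report. The documents give no value, so s is an assumption. With independent reporting, the observed count is binomial with probability s × p1. Power at a true 3.90-fold risk (p1 = 0.078) is P(X ≥ 6 | 100, 0.078 s). The ratio detectable with 80% power is 3.90/s, computed from the unrounded value.

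| Share reported, s | 0.078 s | Power at true 3.90-fold | Detectable ratio |
|---|---|---|---|
| 100% | 7.80% | 80.1% | 3.90 |
| 95% | 7.41% | 75.9% | 4.10 |
| 90% | 7.02% | 71.1% | 4.33 |
| 80% | 6.24% | 59.8% | 4.87 |
| 70% | 5.46% | 46.6% | 5.57 |

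The table holds the reference at 2% and assumes it suffers no similar under-reporting.

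**The case against.** The strongest reply is that the protocol does not confine sites to MCMs. The operational variable list asks for congenital malformations, the specialist reviews all reported anomalies, prenatal test results are collected whatever label is used, and the table is only a summary. The form itself is not shown. This stands in part: it rules out saying that sites report only MCMs as a settled rule. It leaves the inconsistency in place, because a form built from the request and the table would ask for MCMs.

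A second reply is that net bias against the comparator is not shown. Section 8.2 describes EUROCAT as primarily passive surveillance, so the reference may be incomplete too, and the denominator chosen in section 8.7.1 is said to over-estimate risk. This also stands as a limit. It does not change the direction of the site filter, and it does not justify leaving an avoidable loss in place.

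A third reply is that the assumed 10% to 30% loss has no source. That is correct; the power figures show sensitivity and are not an estimate.

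A reader might go further and infer that the registry cannot detect the change seen in animals. Section 6.1 reports "an increase in the incidence rates of a variety of minor skeleton alterations and variants in the offspring at systemic exposure greater than" about 3 times the human exposure at the clinical dose. The documents do not support that inference:
- The same paragraph says that most individual rates stayed within the historical background.
- Section 8.3.2 leaves minor anomalies out of the endpoint on purpose, and section 8.4 limits data to routine care. The wording of the request is therefore not what decides whether such variants are seen.
- Under the broader wording some would be reported.

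**Conclusion.** The point holds as an internal inconsistency with a one-way consequence. If the form follows the narrower wording, site staff make the first major/minor decision, and any true MCM they set aside is lost to the expert and to the numerator. The size is unknown. Under the stated assumptions (independent reporting, reference fixed at 2% and not similarly under-reported), power at a true 3.90-fold risk falls from 80% to 71% with 10% unreported and to 47% with 30% unreported.

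It would be tempting to compare a diluted ratio directly with 3.90 and call the signal missed. That misreads Table 1: 3.90 is the true ratio that gives 80% power, not a threshold for the observed ratio. The rule is 6 or more cases in 100, so an observed 6%, or 3.0-fold, already meets it. Table 1 itself is correct and is not in question.

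**What to change.** In section 8.4, outcome operational definition, and in the MCM row of the table in section 8.6.2.1, ask sites to describe any congenital anomaly noted in the medical record of the infant or foetus. State in section 8.4 that the teratologist/geneticist alone applies the EUROCAT major/minor rule. This brings both places into line with the operational variable list and with the specialist's task.

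The primary MCM endpoint (EUROCAT major only), the sample size and the analyses stay unchanged. A listing of anomalies classed as minor is optional and would be descriptive only, since routine records capture them unevenly.

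The cost is one reworded form item and a few more anomaly descriptions to classify. No test or assessment beyond routine care is added.

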8.5. Study size

The effect sizes that are expected to be detectable were calculated. The effect size is defined as the ratio of the prevalence in exposed patients, estimated from the study, to the prevalence in the reference population. These calculations were performed using a binomial distribution, a power of 80% and a 1-sided Type 1 (false positive) error rate of 5% [Altman, 1991]. Assuming prevalence values in the reference population of 2% (MCMs) and 7.6% (preterm births), 100 exposed live births will be sufficient to detect a 4-fold increase in the risk of MCMs and a 2-fold increase in the risk of pre-term birth, relative to the reference-population prevalence. The calculations were performed using the software PASS (Version 12.0.2, copyright 1983-2013, NCSS, LCC).

Table 1Detectable effect size assuming 80% power

Sample size of live births (N)	PTB reference 7.6% ¹	LBW reference 7.0% ¹	MCM reference 2.00% ²
5	6.45	7.00	24.51
20	4.12	3.69	10.10
50	2.61	2.83	5.38
100	2.05	2.07	3.90
150	1.85	1.91	2.99

Abbreviations: LBW = low birth weight; MCM = major congenital malformations; PTB = preterm birth. ¹Prevalence from Office for National Statistics, 2015 ²Prevalence from EUROCAT, 2017

8.6. Data management

Data for this prospective registry will be managed with an electronic data capture (EDC) platform, which is 21 Code of Federal Regulations (CFR) Part 11 compliant, part of the International Council for Harmonisation (ICH) of Technical Requirements for Pharmaceuticals for Human Use harmonised tripartate agreement. Research staff will provide data by completing an electronic case report form (eCRF) using the OXON proprietary EDC system after informed consent is obtained from the exposed mother. The EDC will have quality standards and checks pre-programmed.

8.6.1. Data handling conventions

Major congenital malformations will be classified using the EUROCAT coding manual [EUROCAT, 2017]. All malformation classifications will be reviewed by a teratologist/geneticist.

All prenatal exposures to medications will be coded using ATC code dictionaries.

8.6.2. Resourcing needs

The implementation, management and closure of this study will be outsourced to a CRO, OXON Epidemiology. The study will be overseen at GSK by a PhD level Epidemiologist and a Study Delivery Lead.

Biostatistical and methodological issues will be addressed by a senior level statistician with expertise in observational data either from the CRO, or similar, or from within GSK.

8.6.2.1.	Timings of Assessment during follow-up
----------	--

Information requested	Registration provided by HCP	Pregnancy outcome provided by research staff up to 3 months post- delivery	Targeted follow up to collect information not previously obtained, provided by research staff
Maternal contact	Х	Xa	
information, alternate			
contact information, HCP			
contact information			
Maternal characteristics	Х		
(age,ethnicity, etc.)			
Maternal prenatal	Х	Xa	
information (LMP, EDD,			
CEDD, prenatal test			
results and timing)			
Obstetrical history	Х		Xp
Family history of MCMs	X		Xb

Information requested	Registration provided by HCP	Pregnancy outcome provided by research staff up to 3 months post- delivery	Targeted follow up to collect information not previously obtained, provided by research staff
IV zanamivir exposure information	X	Xa	
Influenza episode clinical details	X	Xa	
Pregnancy complications	Х	Xa	
Other Concurrent conditions and concomitant medications, tobacco use during pregnancy	X	Xa	
Pregnancy status		Х	
Outcome information (maternal death, live birth, still birth, SAB, gestational age, birth weight)		X	Xp
MCM noted and description		X	Xp

Abbreviations: CEDD = corrected estimated date of deliver; EDD = estimated date of delivery; HCP =health care provider; LMP = last menstrual period; MCM(s) = major congenital malformation(s); Ob =obstetric; SAB = spontaneous abortion.

a Obtain updated information since the previous contact.

b Targeted follow-up is designed to collect addition information (if necessary) to facilitate characterization of the foetal loss, MCMs and/or neonatal death.

8.7. Data analysis

The following approach shall be taken for outcome case management within the registry.

Prospective Registry Reports

The registry will encourage prospective registration, which is defined as registration of a pregnancy exposure prior to knowledge or perceived knowledge of the pregnancy outcome (e.g., structural defect or genetic abnormality noted on a prenatal test).

Prospective reports will be further defined as traditional prospective and pure prospective reports. Traditional prospective reports of pregnancy will include all women who enrol in the registry before the end of pregnancy (live birth, foetal loss, etc), regardless of knowledge of normal or abnormal prenatal test results. Pure prospective reports of pregnancy are a subset of traditional prospective reports and include those where (a) the enrolee did not know at the time of enrolment whether the foetus had adverse outcome such as a malformation, and (b) no prenatal testing was completed prior to enrolment. As the severity of influenza increases with trimester of pregnancy it is likely that most

exposure to IV zanamivir will occur after prenatal screening has occurred. Therefore, in primary analyses, traditional and pure prospective reports will be grouped together.

Data from HCPs that provide de-identified data on all exposed pregnancies in their network will fall into the category of prospective registry reports, as these reports provide objective data on every pregnancy exposure in the network, both positive and negative outcomes. Thus, they avoid the reporting bias inherent in retrospective reporting only after a negative outcome has been noted.

Retrospective Registry Reports

Retrospective reports include subjects for whom the pregnancy outcome has already occurred. Retrospective reports can be biased toward the reporting of more unusual and severe cases and are less likely to be representative of the general population experience than exposures reported prior to knowledge of outcome. Although the exposure can be identified objectives through the UKOSS/INOSS systems, there is still the potential for bias to be introduced if there are delays in the women consenting and between exposure and consent there is additional knowledge of the outcome of the pregnancy. Where possible, the characteristics of prospective and retrospective reports will be compared to assess potential bias. If there is adequate evidence to support lack of bias these prospective and retrospective reports may be combined for analysis, but the initial analysis position will be for retrospective reports with reported MCMs and/or SABs will be reviewed to aid in detection of early signals and listed in registry reports.

Loss to Follow-up

For a prospective report of pregnancy where follow-up information on the pregnancy outcome (live birth, SAB, etc.) is never obtained or is unavailable, the pregnancy will be considered lost to follow-up. Subjects lost prior to pregnancy outcome will be tallied in the registry reports but not included in the statistical analyses.

Duplicate Registry Reports

With registry reports coming from multiple HCPs, it is important to ensure that each case is counted only once [NBDPN, 2004]. Identification of duplicate reports may be problematic for the anonymously reported de-identified cases where there is no specific identifying information. Reports received by the registry will be reviewed for possible duplicate reporting. On receipt of a registration form, the report will be compared with other reports made by the same reporter or compared with other data (such as age, LMP, EDD, and exposure information) to determine if the same report was received previously. If no duplication is identified, the report will be entered in the database. If a duplicate report is later identified through recall or the systematic check for duplicates, the case reported earliest or the one with the most complete data will be maintained as the valid case and updated with any data from the other report not already captured. The duplicate report will be flagged and designated as "Invalid," with the reason being noted as "duplicate report." The criteria for defining a duplicate report will be described ahead of registry operationalisation. Working through the UKOSS/INOSS networks is likely to reduce this problem.

Evaluable Registry Reports

An evaluable report is a subject with data submitted or confirmed by an HCP that contains at least the minimum criteria for a report and is not lost to follow-up. Prospectively reported evaluable subjects with known outcomes will be included in the primary analysis for the registry report. Evaluable retrospective reports will initially be summarized separately in the report (see section on retrospective reports for discussion). Patient-reported data without HCP confirmation will be summarized separately in the report.

Invalid Registry Reports

An invalid registry report is a report for which the minimum data elements are never obtained despite requests for the missing data. If the minimum data are not provided initially, the report will be considered pending until all attempts to resolve queries for missing data and requests for follow-up information are complete. If, after all attempts at follow-up are made, the minimum criteria are still not met, the report will be considered invalid due to insufficient information. Invalid reports will not be included in the registry analyses.

Analysis Population

The primary population for analysis will include all prospective evaluable participants exposed to IV zanamivir that are not lost to follow-up (i.e., participants with appropriate outcome information that meet the minimum criteria for evaluation). Because early prenatal testing is so frequent, it may be difficult to achieve adequate numbers of pure prospectively identified pregnant women if all pregnancies with prior prenatal testing are excluded from the analysis. Therefore, the primary analysis will include pregnancies enrolled prior to birth outcome but after prenatal testing as well (see definitions of prospective reports).

Secondary analyses may consider additional exposure populations captured through deidentified data sources. For example, UKOSS has ethical approval to collect a minimum exposure and outcome dataset on women exposed to new influenza treatments (including IV zanamivir) with a waiver of informed consent. This will enable capture of some data on women who may be exposed to IV zanamivir during hospitalisation with complicated influenza, but do not consent to participate in this study with more complete data collection. The potential and approach for combined analyses of patient populations, dependent on availability of common variables, will be fully described in the Statistical Analysis Plan.

Exclusions for Analysis Purposes

Invalid registry reports and pregnancies deemed lost to follow-up will be excluded from the primary analysis. Initial analyses will consider prospective and retrospective reports separately unless there is adequate evidence to support lack of bias associated with the retrospective reports. If the anti-influenza treatment to which the woman was exposed cannot be ascertained, an unknown exposure cohort will be established and analysed separately.

Sequential Pregnancies

The number and outcome of sequential pregnancies (subsequent pregnancies within the same woman) will be noted and presented. Sequential pregnancies will be included in the analytic dataset.

Multiple Gestation Pregnancies

The number, type (e.g., twin, triplet), and outcome of multiple gestation pregnancies will be noted and presented. Multiple gestation pregnancies will be included in the analytic dataset. These will be counted as multiple outcomes when the denominator is infant births.

